
12.2 Imputation Rules for Missing Prior/Concomitant Medication Dates

Imputation rules for missing or partial medication start/stop dates are defined below:

1. Missing or partial medication start date:
 - a. If only DAY is missing, use the first day of the month.
 - b. If DAY and Month are both missing, use the first day of the year.
 - c. If DAY, Month and Year are all missing, use a date before the first dose date (to impute in practical, use the patient study informed consent date).
2. Missing or partial medication stop date:
 - a. If only DAY is missing, use the last day of the month.
 - b. If DAY and Month are both missing, use the last day of the year.
 - c. If DAY, Month and year are all missing, assign 'continuing' status to stop date (to impute in practical, use the end of study date).

In summary, the prior, concomitant, or post categorization of a medication is described below.

Table 12-2 Prior, Concomitant, and Post Categorization of a Medication

Medication Start Date	Medication Stop Date		
	< First Dose Date of Study Drug	First Dose Date and End Date of TE Period for Patient A	> End Date of TE Period for Patient A
< First dose date of study drug	P	PC	PCA
> First dose date and End date of TE period for Patient A		C	CA
> End date of TE period for Patient A			A

P: Prior; C: Concomitant; A: Post

Same imputation rule will be implemented for missing and/or partial dates of non-pharmacological treatment/procedure.

12.3 Imputation Rules for Missing AE dates

Imputation rules for missing or partial AE start date are defined below. If the imputed AE start date is before the informed consent date for the OLS, the AE start date will be imputed using the informed consent date. Ongoing events from the parent study will follow the imputation rule described in the SAP for parent study.

- **If only Day of AE start date is missing:**

- If the full (or partial) AE end date is NOT before the first dose date of the OLS or AE end date is missing, then
 - if AE start Year and Month are equal to the Year and Month of the first dose date of OLS, then impute the AE start Day as the Day of the first dose date of OLS;
 - else impute the AE start day as 1.
- else impute the AE start day as 1.

- **If Day and Month of AE start date are missing:**

- If the full (or partial) AE end date is NOT before the first dose date of the OLS or AE end date is missing, then
 - if AE start Year is equal to the Year of the first dose date of OLS, then impute the AE start Month and Day as the Month and Day of the first dose date of OLS;
 - else impute the AE start Month as January and Day as 1.
- else impute the AE start Month as January and Day as 1.

- **If Year of AE start date is missing:**

If the Year of AE start date is missing or AE start date is completely missing then query site.

- If the full (or partial) AE end date is NOT before the first dose date of the Treatment Period or AE end date is missing, then impute the AE start date as the first dose date of the OLS.
- else impute the AE start date as the informed consent date.

Compare the imputed AE start date with TE period to determine whether the AE is pre-treatment AE, TEAE or post-treatment AE.

Imputation rules for partial AE end date are defined below:

If partial end date, then impute as min (the last day of the month, data cut-off for IA, end of study) if day is missing, or min (Dec, data cut-off for IA, end of study) if month is missing.

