2.2 Modifications to the Approved Statistical Analysis Plan

This is the 1st version of Statistical Analysis Plan for the interim analysis and final analysis.

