3 INTRODUCTION

VX18-445-110 (Study 110) is a Phase 3, 2-part, open-label extension study of VX18-445-104 (Study 104). For subjects who participate in both Parts A and B, the total study duration is approximately 148 weeks (from the first dose of study drug in this study), including a 96-week Treatment Period in Part A, a 48-week Treatment Period in Part B and a 4-week Safety Follow up Period. The primary objective is to evaluate the long-term safety and tolerability of VX-445 (elexacaftor, ELX)/tezacaftor (TEZ)/ivacaftor (IVA) in subjects with cystic fibrosis (CF) who are heterozygous for the *F508del* mutation and a gating (F/G) or residual function (F/RF) mutation. Safety data will be periodically reviewed by the independent data monitoring committee (DMC).

This SAP (Methods) documents the planned statistical analyses and data presentations of safety and efficacy endpoints for Part A. The SAP will be amended to include Part B prior to Part B DBL. It is based on the most recent approved clinical study protocol (CSP), the most recent approved DMC charter, the most recent approved electronic case report form (eCRF), and the most recent approved eCRF completion guidelines.

Due to the outbreak of COVID-19, to ensure continued safety of subjects who cannot travel to the study sites for their visits (for any reason due to COVID 19), specific alternative measures are being implemented to minimize the risk of exposure to COVID 19. This SAP summarizes the additional statistical analyses that are related to these alternative measures.

The Vertex Biometrics Department will perform the statistical analysis described in this document. SAS (Version 9.4 or higher) will be used to generate all statistical outputs (tables, figures, listings, and datasets). The SAP (Methods) will be finalized and approved prior to IA data lock. Any revisions to the approved SAP will be documented and approved in an amendment to the SAP.

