9.5 Safety Supportive Analysis

9.5.1 Adverse Events of Special Interest

For this study, elevated transaminases events and rash events, as determined by MedDRA Preferred Terms in Appendix F, are considered as adverse events of special interest.

For treatment-emergent elevated transaminases events and rash events, the following categories will be summarized for overall (“Any ELX/TEZ/IVA”):

- Subjects with events
- Subjects with events by maximum severity
- Subjects with events leading to treatment discontinuation
- Subjects with events leading to treatment interruption
- Subjects with serious events
- Subjects with related serious events
- Subjects with events leading to death
- Duration of events
- Time-to-onset of first event (with the first dose date of TC in the OLS as the reference while calculating time-to-onset)

In addition, for treatment-emergent rash events, the above categories will be summarized for the following subgroups:

- Sex (male, female)
- Female subjects with concomitant hormonal therapy (Yes, No)

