10.1 Interim Analysis

As mentioned in the protocol, IA for study 110 may take place at any time during the study at the discretion of the sponsor.

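### Read literally, SAP 12.3 caps partial AE end dates at the interim cut-off in the final analysis too, which would shorten or make negative some durations of rash and transaminase events.

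*SAP*

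**What the plan says.** SAP 12.3 gives one rule for partial AE end dates. If the day is missing, "impute as min (the last day of the month, data cut-off for IA, end of study) if day is missing". The companion rule is "min (Dec, data cut-off for IA, end of study) if month is missing". Neither limits the interim term to interim outputs, and the SAP gives no other AE end-date rule for the final analysis.

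The scope of the plan is set in SAP 2.2: "This is the 1st version of Statistical Analysis Plan for the interim analysis and final analysis". SAP 3 adds that "The SAP (Methods) will be finalized and approved prior to IA data lock", so the text is fixed before the cut-off has served its purpose. The date of the cut-off is open. SAP 10.1 says "IA for study 110 may take place at any time during the study at the discretion of the sponsor", and follow-up includes "a 96-week Treatment Period in Part A".

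AE end dates feed one planned summary. For treatment-emergent elevated-transaminase and rash events, SAP 9.5.1 lists "Duration of events". SAP 9.1 summarises continuous variables by n, mean, SD, median, minimum and maximum.

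**The concern.** When only the day is missing, the month and year of resolution are known. An interim cut-off is a sensible ceiling while the interim analysis is being run, because nothing later has been observed. At the final analysis it is a date in the past. Taking a minimum that still includes it overrides the recorded month and year of any event that resolved later.

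Two errors follow. An event that spans the cut-off loses the part after it. An event that starts after the cut-off is given an end date before its own onset.

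Elevated transaminases and rash are the two event groups of special interest in a study whose primary objective is safety, so the duration summary should be computed from a rule that works at both analyses. The term also has no meaning if no interim analysis is held, and is ambiguous if more than one is held.

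**Working it through.** The plan gives no figure to reproduce. The check applies the rule as written at the final analysis and compares it with the same rule without the interim term.

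**Rules compared**
- As written: end = min(month end or December, interim cut-off, end of study).
- Without the interim term: end = min(month end or December, end of study).
- Duration = end - start + 1. The SAP gives no duration formula, so this is an assumption.

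**Three cases, day of end date missing.** Assumed dates: first dose 15 Jan 2020; interim cut-off 16 Dec 2020 (48 weeks later); end of study 15 Dec 2021 (96 weeks plus 28 days after first dose).

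| AE (true dates) | True duration | As written | Without interim term |
|---|---|---|---|
| 3 Jun to 13 Jun 2020 | 11 | end 30 Jun 2020, 28 days | end 30 Jun 2020, 28 days |
| 1 Dec 2020 to 10 Feb 2021 | 72 | end 16 Dec 2020, 16 days | end 28 Feb 2021, 90 days |
| 10 May to 20 May 2021 | 11 | end 16 Dec 2020, -144 days | end 31 May 2021, 22 days |

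The first event, which ended well before the cut-off, is untouched. The second is truncated. The third ends before it starts. The month-end rule itself overstates duration somewhat (28 for 11, 90 for 72, 22 for 11), so the understatement comes from the interim term alone.

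**Effect on a summary mean.** Assumed: 20 events, 19 lasting 15 days each (sum 19 × 15 = 285), and one rash with onset on Day 500, true duration 21 days and end day missing. The cut-off is placed at the Week 24, 48 or 72 target day in SAP Table 12-1 (Days 169, 337, 505).

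| Cut-off | Duration as written | Mean of 20 |
|---|---|---|
| Day 169 | 169 - 500 + 1 = -330 | (285 - 330)/20 = -2.25 |
| Day 337 | 337 - 500 + 1 = -162 | (285 - 162)/20 = 6.15 |
| Day 505 | 505 - 500 + 1 = 6 | (285 + 6)/20 = 14.55 |

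The right comparator is what the corrected rule would give, not the true 21 days. Month-end imputation adds 0 to 30 days, so the duration is 21 to 51 days and the mean is (285 + 21)/20 = 15.3 to (285 + 51)/20 = 16.8. The median is 15 in every case. The minimum is 15 without the interim term, and -330, -162 or 6 as written.

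**Share affected, among partial end dates only.** If onset is uniform over 96 weeks, the share starting after a cut-off at week w is 1 - w/96: 75%, 50% and 25% for weeks 24, 48 and 72. All of these would end before they start. A simulation in which every event lacks its end day gave the same shares. These shares say nothing about how many AEs have partial end dates, and the documents do not give that number.

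**What does not move.** Classification uses the start date: "Compare the imputed AE start date with TE period to determine whether the AE is pre-treatment AE, TEAE or post-treatment AE". The start-date rules in SAP 12.3 look at the recorded full or partial end date, not the imputed one. Counts, percentages, exposure-adjusted rates and time to onset need no imputed end date.

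**The case against.** The strongest reply is that a cut-off named for the interim analysis naturally binds only when that analysis is run. That was probably the intent. SAP 12.1 uses a generic data cut-off when the last dose date is unavailable, which fits a cut-off tied to the analysis in hand, and a negative duration would be conspicuous in programming checks. This stands as far as it goes: a reader might infer that later events will be given end dates before their onset, and the documents support that only on a literal reading. It does not remove the defect. The SAP separates the two analyses where it means to (SAP 9.2.7 confines important protocol deviations to the final analysis), and the medication stop-date rule in SAP 12.2 has no interim term. A programmer who did the sensible thing would be departing from the written rule.

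The second reply is that the reach is narrow. It is: one descriptive item, for two event groups, in a supportive section. Protocol 13.1.1.3 collects the resolution date of each AE and Protocol 13.3 has missing or discrepant data queried, so partial dates may be few. Neither provision corrects the rule.

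A reader might also infer that the lack of a floor at the AE start date is a second fault. It is not. Month end or December of the recorded end period cannot precede a valid start. End of study is the last subject's last scheduled contact (Protocol 13.2.8), while AEs are collected only through each subject's participation. Negative durations come from the interim term alone.

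**Conclusion.** The rule is wrong as written, and the point is minor. Applied literally at the final analysis, it truncates the duration of events that span the interim cut-off and gives events that start later an end before their onset, whenever the end date is partial. The damage is confined to the mean and minimum, and much less the median, of the duration summaries for elevated transaminases and rash. The documents do not support a wider claim that TEAE status, event counts, rates or time to onset are distorted.

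The size cannot be stated from the documents. It depends on when an interim analysis is held, how many events of special interest have partial end dates after the cut-off, and whether the programmer follows the text. The effect is zero if there are no such dates. The worked figures rest wholly on assumed dates, onset days, event counts and durations. They show the direction and the possible size per event, not an expected impact. The cut-off is also a calendar date, so it falls on a different study day for each subject.

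**What to change.** In the AE end-date sentence of SAP 12.3, replace the interim cut-off with the data cut-off for the analysis being run. The rule becomes: min(last day of the month, or December if the month is missing; data cut-off for the analysis being run; end of study). The interim cut-off then does not apply at the final analysis, and the wording also covers no interim analysis or several.

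Keep end of study as the last term. Changing it to the end of a subject's participation is not needed and could do harm: Protocol 13.1.1.7 follows AEs to a final outcome, so a resolution date may fall after participation ends (Protocol 9.1.5) and would be cut off.

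A programming check that no imputed end date precedes the AE start date is an optional safeguard.

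The cost is one phrase in a SAP amendment, with no new data. SAP 3 already requires revisions to be documented in an amendment and plans one for Part B, but this change should be in place before the Part A final analysis.

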12.4 Criteria for Threshold Analysis

Table 12-3 Threshold Analysis Criteria for Laboratory Tests (as applicable)

Parameter	Threshold Analysis	Comments
Clinical Chemistry (LFT)		
ALT	>ULN – ≤3×ULN >3× – ≤5×ULN >5× – ≤8×ULN >8× – ≤20×ULN >20.0×ULN	FDA DILI Guidance Jul 2009.
AST	>ULN – ≤3×ULN >3× – ≤5×ULN >5× – ≤8×ULN >8× – ≤20×ULN >20.0×ULN	FDA DILI Guidance Jul 2009.
ALT or AST	(ALT >ULN – ≤3×ULN) or (AST >ULN – ≤3×ULN) (ALT >3× – ≤5×ULN) or (AST >3× – ≤5×ULN) (ALT >5× – ≤8×ULN) or (AST >5× – ≤8×ULN) (ALT >8× – ≤20×ULN) or (AST >8× – ≤20×ULN) ALT >20×ULN or AST >20×ULN	FDA DILI Guidance
Alkaline Phosphatase	>ULN – ≤1.5×ULN >1.5× – ≤2.5×ULN >2.5× – ≤5×ULN >5× – ≤20×ULN >20×ULN	FDA DILI Guidance Jul 2009.
Total Bilirubin	>ULN – ≤1.5×ULN >1.5× – ≤2×ULN >2× – ≤3×ULN >3× – ≤10×ULN >10×ULN	FDA DILI Guidance Jul 2009.
Direct Bilirubin	>ULN – ≤1.5×ULN >1.5× – ≤2×ULN >2× – ≤3×ULN >3× – ≤10×ULN >10×ULN	FDA DILI Guidance Jul 2009.
Indirect Bilirubin	>ULN – ≤1.5×ULN >1.5× – ≤2×ULN >2× – ≤3×ULN >3× – ≤10×ULN >10×ULN	FDA DILI Guidance Jul 2009.
ALT and Total Bilirubin	ALT >3×ULN and TBILI >2×ULN	FDA DILI Guidance Jul 2009.
AST and Total Bilirubin	AST >3×ULN and TBILI >2×ULN	FDA DILI Guidance Jul 2009.

Table 12-3 Threshold Analysis Criteria for Laboratory Tests (as applicable)

Parameter	Threshold Analysis	Comments
(ALT or AST) and Total Bilirubin	(ALT >3×ULN or AST >3×ULN) and TBILI >2×ULN	FDA DILI Guidance Jul 2009.
GGT	>ULN – ≤ 2.5×ULN >2.5× – ≤ 5.0×ULN >5.0× – ≤ 20.0×ULN >20.0×ULN	CTCAE grade 1-4
Clinical Chemistry (NON-LFT)		
Albumin	<LLN – ≥ 30 g/L <30 – ≥ 20 g/L <20 g/L	CTCAE grade 1-3
Amylase	>ULN – ≤ 1.5×ULN >1.5× – ≤ 2×ULN >2× – ≤ 5×ULN >5×ULN	Criteria based upon CTCAE
Creatinine	>ULN – ≤ 1.5×ULN >1.5× – ≤ 3.0×ULN >3.0× – ≤ 6.0×ULN >6.0×ULN	CTCAE grades 1-4
Lipase	>ULN – ≤ 1.5×ULN >1.5× – ≤ 2×ULN >2× – ≤ 5×ULN >5×ULN	Criteria based upon CTCAE
Total protein	<LLN >ULN	No CTCAE
Creatine Kinase	>ULN – ≤ 2.5×ULN >2.5× – ≤ 5×ULN >5× – ≤ 10×ULN >10×ULN	CTCAE grades 1-4
Hematology		
Hemoglobin	Hgb decreased (anemia) <LLN – ≥ 100 g/L <100 – ≥ 80 g/L < 80 g/L	CTCAE grade 1-3
	Hgb increased >ULN – ≤ 20 g/L above ULN >20 g/L above ULN – ≤ 40 g/L above ULN >40 g/L above ULN	CTCAE grade 1-3
Platelets	Platelet decreased <LLN – ≥ 75.0×10e9 /L <75.0× – ≥ 50.0×10e9 /L <50.0× – ≥ 25.0×10e9 /L <25.0 × 10e9 /L	CTCAE grade 1-4
	Platelet increased >ULN	No CTCAE available

Table 12-3 Threshold Analysis Criteria for Laboratory Tests (as applicable)

Parameter	Threshold Analysis	Comments
Reticulocytes/Erythrocytes (%)	<LLN >ULN	No CTCAE
Coagulation		
Activated partial thromboplastin time (PTT)	>ULN – ≤ 1.5×ULN >1.5× – ≤ 2.5×ULN >2.5×ULN	CTCAE grade 1-3
Prothrombin time (PT) International Normalized Ratio (INR)	>ULN – ≤ 1.5×ULN >1.5× – ≤ 2.5×ULN >2.5×ULN	CTCAE grade 1-3

Table 12-4 Threshold Analysis Criteria for Laboratory Tests (for labeling purpose)

Parameter	Threshold Analysis	Comments
Clinical Chemistry (LFT)		
ALT or AST	>3×ULN >5×ULN >8×ULN	For labeling purpose

Table 12-5 Threshold Analysis Criteria for ECGs

Parameter	Threshold Analysis	Comments
HR	Bradycardia <50 bpm <45 bpm Decrease from baseline ≥10 bpm Decrease from baseline ≥20 bpm <50 bpm and decrease from baseline ≥10 bpm <50 bpm and decrease from baseline ≥20 bpm	Per HV grade 2, 3, plus shift change
	Tachycardia >100 bpm >115 bpm >130 bpm Increase from baseline ≥10 bpm Increase from baseline ≥20 bpm >100 bpm and increase from baseline ≥10 bpm >100 bpm and increase from baseline ≥20 bpm	
PR	≥240 ms ≥300 ms ≥200 ms and increase from baseline ≥40 ms ≥200 ms and increase from baseline ≥100 ms	

Table 12-5 Threshold Analysis Criteria for ECGs

Parameter	Threshold Analysis	Comments
QRS	>110 ms >160 ms Increase from baseline \geq 20 ms Increase from baseline \geq 40 ms	
QTc Borderline Prolonged* Additional	>450 ms and <500ms (Male); >470 ms and <500ms (Female) \geq 500 ms Increase from baseline Increase from baseline >10 ms Increase from baseline >20 ms Increase from baseline >40 ms Increase from baseline >60 ms	To be applied to any kind of QT correction formula.

Note: Based on CPMP 1997 guideline.

Table 12-6 Threshold Analysis Criteria for Vital Signs

Parameter	Threshold Analysis	Comments
Pulse Rate	Same as above in ECG category	
SBP increased	>140 mmHg >160 mmHg >10 mmHg increase from baseline >20 mmHg increase from baseline >140 mmHg & >10 mmHg increase from baseline >140 mmHg & >20 mmHg increase from baseline >160 mmHg & >10 mmHg increase from baseline >160 mmHg & >20 mmHg increase from baseline	809/770 analyses
SBP decrease	<90 mmHg <80 mmHg >10 mmHg decrease from baseline >20 mmHg decrease from baseline <90 mmHg and >10 mmHg decrease from baseline <90 mmHg and >20 mmHg decrease from baseline <80 mmHg and >10 mmHg decrease from baseline <80 mmHg and >20 mmHg decrease from baseline	Per HV grade 1, 3, plus shift change

Table 12-6 Threshold Analysis Criteria for Vital Signs

Parameter	Threshold Analysis	Comments
DBP increased	>90 mmHg >100 mmHg >5 mmHg increase from baseline >10 mmHg increase from baseline	
	>90 mmHg and >5 mmHg increase from baseline >90 mmHg and >10 mmHg increase from baseline >100 mmHg and >5 mmHg increase from baseline >100 mmHg and >10 mmHg increase from baseline	
DBP decreased	<60 mmHg <45 mmHg >5 mmHg decrease from baseline >10 mmHg decrease from baseline	
	<60 mmHg and >5 mmHg decrease from baseline <60 mmHg and >10 mmHg decrease from baseline <45 mmHg and >5 mmHg decrease from baseline <45 mmHg and >10 mmHg decrease from baseline	
Weight	Weight gain ≥5 % increase from baseline ≥10 % increase from baseline ≥ 20% increase from baseline	CTCAE grade 1-3
	Weight loss ≥5 % decrease from baseline ≥10 % decrease from baseline ≥ 20% decrease from baseline	CTCAE grade 1-3

12.5 Details of GLI Equations for Calculating ppFEV₁

Percent predicted values will be calculated for parameters of FEV₁, FVC, FEV₁/FVC, and FEF_{25%-75%} using the Quanjer GLI-2012 Regression Equations and Lookup Tables. Details of the derivation of the GLI equation are provided in the article by Quanjer et al. (2012).

The regression equations and lookup tables required to implement the Quanjer GLI-2012 predicted values are available in:

Philip H. Quanjer, Sanja Stanojevic, Tim J. Cole, Janet Stocks. Quanjer GLI-2012 Regression Equation and Lookup Tables (Version 7 April 2013). Global Lung Function Initiative. [online] Available at: <https://www.ers-education.org/lr/show-details/?idP=138978> [Accessed September 09, 2020].

The instructions and tools on how to implement the Quanjer GLI-2012 equations are:

Philip H. Quanjer, Sanja Stanojevic, Tim J. Cole, Janet Stocks. Implementing GLI-2012 regression equations (Version 19 July 2015). Global Lung Function Initiative. [online] Available at: <https://www.ers-education.org/lr/show-details/?idP=138979> [Accessed September 09, 2020].

Sanja Stanojevic. GLI-2012 - SAS Macro (Version 2, 7 April 2013). Global Lung Function Initiative. [online] Available at: <https://www.ers-education.org/lr/show-details/?idP=138988> [Accessed September 09, 2020].

Data handling rule for spirometry is as follows:

- Input age and height with at least 2 decimal place
- For subjects whose age at informed consent of the parent study is >21 years, height at screening of the parent study is used regardless if height is collected at other study visits. For subjects whose age at informed consent of the parent study is ≤21 years, height collected at the respective visit is used, and if the height at the respective visit is not available, the last non-missing record will be used.
- For race, map CRF race – “black or AA” to “black”, map all other CRF races (except white) to “other”; multiple checks for race in CRF are also mapped to “other”; white is a reference race in the equations and assumes 0 values for all race coefficients in the GLI equations.
